Appendix 3 Pandemic Risk Assessment and Mitigation Plan

During an ongoing pandemic, potential risks associated with patients being unable to attend study visits have been identified for this study.

These potential risks and mitigation plans can be summarized as follows:

1) Schedule of assessments:

- a) Physical examination:
 - i) For all assessments where a physical examination is indicated, this portion of the visit can be conducted virtually; however, when samples need to be collected or dosing performed, these activities must occur in the clinic.
 - ii) If a virtual visit is conducted for the physical examination assessment portion, in order to limit a patient's time in the clinic, vital signs may be omitted.

b) Dosing:

- i) For Cycle 2 and repriming cycles, magrolimab can be administered on Day 7 with azacitidine, with collection of Day 8 assessments (ie, laboratory assessments, PK) on Day 7 in order to minimize an extra patient visit.
- ii) Dosing delays with magrolimab:
 - (1) For patients who may have travel restrictions, the 4-week period of magrolimab dose delay for repriming can be extended to 6 weeks in order to minimize the need for repriming for patients in this scenario. Medical monitor approval is needed for this specific situation. Magrolimab every-2-week dosing should be encouraged as dosing intervals longer than this will lead to suboptimal efficacy.

iii) Dosing with azacitidine:

- (1) If needed under specific circumstances, sites can allow for administration of azacitidine locally nearer to patient's residence, with proper documentation (eg, name of site, name of physician overseeing transfusion, name of laboratory used, including accreditation certificate). Administration of azacitidine outside the center should be reserved only in cases where patients will not be able to get azacitidine dosing otherwise.
- (2) If treatment administration is given locally, then the patient should be evaluated by a local hematologist on Day 1 of that treatment cycle and have all laboratory assessments required on the Day 1 treatment cycle performed as per the protocol. The site should procure the clinical notes and laboratory reports for the principal investigator (PI) review and signature. The site is to ensure that all of these documents are filed in the patient's source records.

(3) The treating physician at the study site should speak to the local hematologist and review protocol guidelines/dosing of azacitidine/reporting of reactions and document this information in the medical records.

c) Sample collection:

- i) While it is preferred to collect all protocol-specified laboratory samples, if resources are limited, PK/ADA samples may be collected and stored (frozen) and not shipped in real-time if staff are not available to do so.
- ii) MRD testing should be collected and shipped in real-time.
- iii) For correlative peripheral blood or bone marrow aspirate samples, if they cannot be shipped according to their corresponding standard procedures same day, or refrigerated overnight for shipment the next day, please isolate the mononuclear cells (eg, by Ficoll gradient) and cryopreserve according to local best practices. If it is not possible to either ship samples or preserve and store according to the guidance above, then collection of these samples may be omitted until normal operations can resume.
- d) General patient selection guidance:
 - To minimize patients receiving RBC transfusions given the current transfusion product shortage, we recommend selecting patients with higher hemoglobin thresholds at baseline and use IV iron and/or erythropoietin where clinically indicated.
- 2) Study drug supplies to patients and sites:
 - a) Patients may be unable to return to the site for a number of visits to get the study drug, or the site may be unable to accept any patient visits. Without study drugs, the patient would not be able to stay on the study drug as planned per protocol.
 - Mitigation plan: If permitted by local EC/IRB/Regulatory authority as applicable and with sponsor's approval, study drug supplies may be provided to the patient from the site without a clinic visit. It must be confirmed that the patient may safely continue on study drug as determined by the PI. A virtual study visit, via phone or video conferencing, must be performed prior to remote study drug resupply. At the earliest opportunity, the site will schedule in-person patient visits and return to the protocol's regular schedule of assessments. A qualified courier may be utilized to ship the study drug from sites to study patients, and a qualified vendor may be utilized to perform infusions in the patients' local vicinity.
 - b) Shipments of study drug from the sponsor to the investigational site could be delayed because of transportation issues. Without study drug, the patient would not be able to stay on the study drug as planned per protocol.

CONFIDENTIAL Page 148 02 November 2023

Mitigation plan: The sites' study drug inventory should be closely monitored. Site staff should notify the sponsor or delegate if they foresee shortage in study drug inventory or if there is any interruption in local shipping service. The sponsor will continue to monitor inventory at the study drug depot and study sites. Manual shipments will be triggered as necessary.

- 3) Patient safety monitoring and follow-up:
 - a) Patients may be unable or unwilling to come to the study site for their scheduled study visits as required per protocol.

Mitigation plan: For patients who may be unable or unwilling to visit the study site for their scheduled study visits as required per protocol, the PI or qualified delegate will conduct a virtual study visit, via phone or video conferencing, to assess the patient within target visit window date whenever possible. During the virtual study visit, the following information at minimum will be reviewed:

- i) Confirm if patient has experienced any AEs/serious adverse events (SAEs)/special situations (including pregnancy) and follow-up on any unresolved AE/SAEs
- ii) Review current list of concomitant medications and document any new concomitant medications
- iii) If applicable, confirm patient's study drug supply is sufficient to last until the next planned visit date. If study drug resupply is needed it will be provided as described above in (2)
- iv) If applicable, confirm that electronic diary questionnaires and patient-reported outcomes have been completed and transmitted
- v) If applicable, remind patient to maintain current dosing and to keep all dispensed study drug kits for return at the next on-site visit
- b) Patients may be unable or unwilling to travel to the site for planned assessments (eg, safety blood draws); hence, samples may not be sent for central laboratory analyses.
 - Mitigation plan: Accredited local laboratory may be utilized as appropriate to monitor patient safety until the patient can return to the site for their regular follow-up per protocol. Any laboratory assessments conducted at a local laboratory due to the pandemic will be documented accordingly. Pregnancy testing may be performed using a home urine pregnancy test if local laboratory pregnancy testing is not feasible. Alternative sample handling and storage may be possible for samples routinely sent to the central laboratory; sites should refer to the study laboratory manual and discuss with the sponsor for further guidance.
- c) Patients may be unable or unwilling to attend the study visit to sign an updated ICF version if there is an update.

Mitigation plan: The site staff will follow their approved consent process and remain in compliance with local EC/IRB and national laws and regulations. Remote consent will be allowed if it has been approved by the local EC/IRB. The consent process will be documented and confirmed by normal consent procedure at the earliest opportunity.

d) The safety of trial patients is important and testing of COVID-19 infection will be based on local clinical guidelines for testing based on signs/symptoms and or suspected exposure to COVID-19.

Mitigation plan: If patient has a diagnosis of COVID-19 while on this clinical study, study drugs may be held until clinical improvement or resolution in accordance with the treating physician's judgment and general magrolimab/azacitidine dose delay guidance in the protocol. Additional supportive care and treatment measures for COVID-19 infection on the study will be performed in accordance with local institutional guidelines. Patients with a COVID-19 infection while participating in a clinical trial will have this event documented as an adverse event in the clinical database.

- 4) Protocol and monitoring compliance:
 - a) Protocol deviations may occur if scheduled visits cannot occur as planned per protocol.

Mitigation plan: If it is not possible to complete a required procedure, an unscheduled visit should be conducted as soon as possible when conditions allow. The situation should be recorded and explained as a protocol deviation. Any missed patient visits or deviation to the protocol due to the pandemic must be reported in the eCRF and described in the clinical study report (CSR). Any virtual study visits that are conducted in lieu of clinic visits due to the pandemic will be documented as a protocol deviation related to the pandemic.

b) Monitors may be unable to carry out source data review or source data verification (SDV), or study drug accountability or assess protocol and GCP compliance. This may lead to delays in SDV, an increase in protocol deviations, or under reporting of AEs.

Mitigation plan: The study monitor is to remain in close communication with the site to ensure data entry and query resolution. The study monitor is to reference the Study Monitoring Plan for guidance on how to conduct a remote monitoring visit. The study staff is to save and document all relevant communication in the study files. The status of sites that cannot accept monitoring visits and/or patients on site, must be tracked centrally and updated on a regular basis.

- 5) Missing data and data integrity:
 - a) There may be an increased amount of missing data due to patients missing visits/assessments. This could have an impact on the analysis and the interpretation of clinical study data.

Mitigation plan: Implications of a pandemic on methodological aspects for the study will be thoroughly assessed and documented, and relevant actions will be taken as appropriate (ie, modification of the statistical analysis plan) and in compliance with regulatory authorities' guidance. Overall, the CSR will describe the impact of the pandemic on the interpretability of study data.

Risks will be assessed continuously, and temporary measures will be implemented to mitigate these risks as part of a mitigation plan, as described above. These measures will be communicated to the relevant stakeholders as appropriate and are intended to provide alternate methods that will ensure the evaluation and assessment of the safety of patients who are enrolled in this study.

Since these potential risks are considered mitigated with the implementation of these measures, the expected benefit-risk assessment of the study drugs in study patients remains unchanged. In the event that these potential risks cannot be mitigated due to the escalation of a pandemic, randomization of new patients will be placed on hold until the pandemic outbreak is under control by following local regulatory guidelines.

Appendix 4. Toxicity Grading Scale for Severity of Adverse Events and Laboratory Abnormalities

 $https://ctep.cancer.gov/protocolDevelopment/electronic_applications/docs/CTCAE_v5_Quick_R\\ eference_8.5x11.pdf$

Appendix 5. Pregnancy Precautions, Definition for Female of Childbearing Potential, and Contraceptive Requirements

1) Definitions

a) Definition of Childbearing Potential

For the purposes of this study, a female born patient is considered of childbearing potential following the initiation of puberty (Tanner stage 2) until becoming post-menopausal, unless the patient is permanently sterile or has medically documented ovarian failure.

Women are considered to be in a postmenopausal state when they are ≥ 54 years of age with cessation of previously occurring menses for ≥ 12 months without an alternative cause. In addition, women of < 54 years of age with amenorrhea of ≥ 12 months may also be considered postmenopausal if their follicle-stimulating hormone level is in the postmenopausal range and they are not using hormonal contraception or hormonal replacement therapy.

Permanent sterilization includes hysterectomy, bilateral oophorectomy, or bilateral salpingectomy in a female patient of any age.

b) Definition of Male Fertility

For the purposes of this study, a male-born patient is considered to be fertile after the initiation of puberty unless the patient is permanently sterile by bilateral orchidectomy or medical documentation.

2) Contraception Requirements for Female Patients

a) Study Drug Effects on Pregnancy and Hormonal Contraception

Magrolimab is contraindicated in pregnancy as a higher incidence of total pregnancy loss has been observed in and embryo-fetal development toxicity study in cynomolgus monkeys and there is a strong suspicion of human fetotoxicity in early pregnancy based on the nonclinical data. For magrolimab, there is no anticipated PK interaction with progestin or other steroids based on the distinct clearance pathways.

Based on the mechanism of action (MOA) and findings in animals, azacitidine may cause fetal harm when administered to a pregnant woman. Advise females with reproductive potential to avoid pregnancy during treatment with azacitidine. Studies in vitro have demonstrated that CYP enzyme induction or inhibition by azacitidine at clinically achievable plasma concentrations is unlikely.

Based on its MOA and findings in animals, venetoclax may cause embryo-fetal harm when administered to a pregnant woman. Advise females with reproductive potential to avoid pregnancy during treatment with venetoclax. It is currently unknown whether venetoclax may reduce the effectiveness of hormonal contraceptives.

Based on its MOA and findings in animals, mitoxantrone may cause fetal harm when administered to a pregnant woman. Women of childbearing potential should be advised to avoid becoming pregnant. Women treated with mitoxantrone have an increased risk of transitory or persistent amenorrhea. To date, post-marketing experience has not revealed any significant drug interactions in patients who have received mitoxantrone for treatment of cancer.

Based on animal studies and its MOA, etoposide can cause fetal harm when administered to a pregnant woman. Women of childbearing potential should be advised to avoid becoming pregnant.

Cytarabine can cause fetal harm when administered to a pregnant woman. Women of childbearing potential should be advised to avoid becoming pregnant.

Based on the MOA and findings in animals, CC-486 (Onureg) can cause fetal harm when administered to a pregnant woman. Based on animal data, CC-486 (Onureg) may impair female fertility. Studies in vitro have demonstrated that CYP enzyme induction or inhibition by azacitidine at clinically achievable plasma concentrations is unlikely.

Refer to the latest version of the magrolimab IB for additional information. Refer to the regional prescribing information for information on the potential risks of treatment with azacitidine {VIDAZA 2018}, venetoclax {VENCLEXTA 2020}, mitoxantrone {MitoXANTRONE 2018}, etoposide {ETOPOPHOS 2019}, cytarabine {CYTARABINE 2020}, and CC-486 {ONUREG 2020}.

b) Contraception Requirements for Female Patients of Childbearing Potential

The inclusion of female patients of childbearing potential requires the use of highly effective contraceptive measures with a failure rate of < 1% per year. They must have a negative serum pregnancy test at screening and a negative pregnancy test is required prior to study treatment administration on Cycle 1 Day 1. Pregnancy tests will be performed every 4 weeks thereafter (described in the protocol) until the end of contraception requirement.

Duration of required contraception for female patients in this clinical trial should start from screening visit until 6 months after the last dose of the latest administered study drug.

Female patients must agree to one of the following contraceptive methods:

Complete abstinence from intercourse of reproductive potential. Abstinence is an acceptable method of contraception only when it is in line with the patient's preferred and usual lifestyle.

Or

Consistent and correct use of 1 of the following methods of birth control listed below:

- Non-hormonal intrauterine device (IUD)
- Hormonal IUD (must be used in conjunction with a barrier method)

- Bilateral tubal occlusion (upon medical assessment of surgical success)
- Vasectomy in the male partner (upon medical assessment of surgical success)

Or

Female patients who wish to use a hormonally based method must use it in conjunction with a barrier method, preferably a male condom. Hormonal methods are restricted to those associated with the inhibition of ovulation. Hormonally based contraceptives and barrier methods permitted for use in this protocol are as follows, where local standard of care practices allow:

- Hormonal methods (each method must be used with a barrier method, preferably male condom)
 - Oral contraceptives (either combined or progesterone only)
 - Injectable progesterone
 - Transdermal contraceptive patch
 - Contraceptive vaginal ring
 - Subdermal contraceptive implant
- Barrier methods (each method must be used with a hormonal method)
 - Male condom (with or without spermicide)
 - Female condom (with or without spermicide)
 - Diaphragm with spermicide
 - Cervical cap with spermicide
 - Sponge with spermicide

Inclusion of methods of contraception in this list of permitted methods does not imply that the method is approved in any country or region. Methods should only be used if locally approved.

Female patients must also refrain from egg donation, cryopreservation of cells, and in vitro fertilization during treatment and until the end of contraception requirement. If needed, female patients should be advised to seek advice about egg donation and cryopreservation prior to treatment.

3) Contraception Requirements for Male Patients

Male patients with female partners of childbearing potential must use condoms during treatment and until 6 months after the last dose of the latest administered companion drug. If the female partner of childbearing potential is not pregnant, use of any locally approved contraceptive method should also be considered. Based on companion drugs, male patients must also refrain from sperm donation and cryopreservation of cells during treatment and until the end of contraception requirement for the companion drug. If needed, male patients should be advised to seek advice about sperm donation and cryopreservation prior to treatment.

4) Unacceptable Birth Control Methods

Birth control methods that are unacceptable include periodic abstinence (eg, calendar, ovulation, symptothermal, post-ovulation methods), withdrawal (coitus interruptus), spermicides only, and lactational amenorrhea method. A female condom and a male condom should not be used together.

5) Procedures to Be Followed in the Event of Pregnancy

Female patients will be instructed to notify the investigator if they become pregnant or suspect they are pregnant at any time from start of the study to 6 months post last study drug dose. Study drug must be discontinued immediately.

Male patients whose partner has become pregnant or suspects she is pregnant from start of study to 6 months post last study drug dose must also report the information to the investigator. Instructions for reporting pregnancy and pregnancy outcome are outlined in Section 7.4.2.3.

Appendix Table 11. Additional Response Definitions Used in This Study (2003 IWG Criteria)

	Definitions						
Response Criteria	Neutrophils	Platelets	Bone Marrow Blasts	Other			
Cytogenetic CR (cCR)	> 1.0 × 10 ⁹ /L	> 100 × 10 ⁹ /L	< 5%	Cytogenetics normal and no evidence of extramedullary disease			

cCR = cytogenetic complete remission; CR = complete remission; IWG = International Working Group Source: {Cheson 2003}

Treatment Failure

Treatment failure is defined as failure to achieve complete remission (CR) before the fifth cycle of magrolimab+venetoclax+azacitidine in Cohort 1 and before the third cycle of magrolimab + MEC in Cohort 2.

a Not in the ELN 2017 guidelines. Modification for the purpose of this protocol. A response could be classified as both CRh and CRi if both criteria are met.

Appendix 8. Cockcroft-Gault Method for Estimating Creatinine Clearance

Formulas for calculating the estimated creatinine clearance (eC_{cr}) are provided in the table below. The formula appropriate to the units in which serum creatinine was measured and the patient's gender should be used.

Serum Creatinine Units	Gender			Formula
mg/dL	Males	eC _{cr} = [mL/min]	= -	(140-subject age [years]) × subject weight [kilograms] × 1 72 × subject serum creatinine [mg/dl]
	Females	eC _{cr} = [mL/min]	= _	(140-subject age [years]) × subject weight [kilograms] × 0.85 72 × subject serum creatinine [mg/dl]
μM/dL	Males	eC _{cr} = [mL/min]	= -	(140-subject age [years]) × subject weight [kilograms] × 1.23 Subject serum creatinine [mg/dl]
	Females	eC _{cr} =	= _	(140-subject age [years]) × subject weight [kilograms] × 1.04 Subject serum creatinine [mg/dl]

 eC_{cr} =estimated creatinine clearance

Source: {Cockcroft 1976}

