4.2. Inclusion Criteria

All Patients

All patients must meet the following inclusion criteria to be eligible for participation in this study:

1) White blood cell (WBC) count $\leq 20 \times 10^3/\mu L$ prior to first dose of study treatment. If the patient's WBC count is $\geq 20 \times 10^3/\mu L$ prior to first dose of study treatment, the patient can be enrolled, assuming all other eligibility criteria are met. However, ensure that the WBC count is $\leq 20 \times 10^3/\mu L$ prior to the first dose of study treatment and prior to each magnolimab dose for the first 4 weeks.

NOTE: Patients can be treated with hydroxyurea and/or leukapheresis throughout the study or prior to first dose of study treatment to reduce the WBC count to $\leq 20 \times 10^3/\mu L$ to enable eligibility for magrolimab dosing.

2) Hb must be ≥ 9 g/dL prior to initial dose of study treatment

NOTE: Transfusions are allowed to meet Hb eligibility (see Section 7.8.1.1).

- 3) Adequate liver function as demonstrated by the following:
 - a) AST $\leq 3.0 \times$ upper limit of normal (ULN)
 - b) ALT $\leq 3.0 \times ULN$
 - c) bilirubin $\leq 1.5 \times \text{ULN}$, or $\leq 3.0 \times \text{ULN}$ and primarily unconjugated if patient has a documented history of Gilbert syndrome or genetic equivalent.
- 4) Patients must have adequate renal function as demonstrated by a creatinine clearance (CLcr) ≥ 30 mL/min calculated by the Cockcroft-Gault formula.
- 5) Patient has provided informed consent.
- 6) Patient is willing and able to comply with clinic visits and procedures outlined in the study protocol.
- 7) Male or female, age \geq 18 years.
- 8) Pretreatment blood cross-match completed (as detailed in Section 6.5.3).
- 9) Male patients and female patients of childbearing potential who engage in heterosexual intercourse must agree to use protocol-specified method(s) of contraception as described in Appendix 5.
- 10) Patients must be willing to consent to mandatory pretreatment and on-treatment bone marrow biopsies (trephines), unless not feasible as determined by the investigator and discussed with the sponsor.

Safety Run-in Cohort 1 and Phase 2 Cohort 1 (1L Unfit AML Mag+Ven+Aza), closed to enrollment globally as of Protocol Amendment 5

In addition to meeting the inclusion criteria for all patients, patients who are enrolled into Safety Run-in Cohort 1 and Phase 2 Cohort 1 must fulfill the following cohort-specific inclusion criteria:

CONFIDENTIAL Page 61 02 November 2023

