
- 11) Newly diagnosed, previously untreated patients with confirmation of AML by WHO criteria who are ineligible for treatment with a standard cytarabine and anthracycline induction regimen due to age, comorbidity, or other factors. Patients must be considered ineligible for induction therapy defined by the following:
 - a) ≥ 75 years of age
 - b) \geq 18 to 74 years of age with at least 1 of the following comorbidities:
 - i. ECOG performance status of 2 or 3
 - ii. Diffusing capacity of the lung of carbon monoxide $\leq 65\%$ or forced expiratory volume in 1 second $\leq 65\%$
 - iii. LVEF $\leq 50\%$
 - iv. CLcr < 45 mL/min calculated by the Cockcroft-Gault formula
 - v. Any other comorbidity that the investigator judges to be incompatible with intensive chemotherapy that must be approved by the sponsor medical monitor before study enrollment.
- 12) ECOG performance status:
 - Of 0 to 2 for subjects \geq 75 years of age

OR

- Of 0 to 3 for subjects \geq 18 to 74 years of age
- 13) Patients who have not received prior anti-leukemia therapy for AML (excluding hydroxyurea), HMA, low-dose cytarabine, and/or venetoclax.
 - NOTE: Patients with prior MDS who have not received prior HMA, venetoclax, or a chemotherapeutic agent are eligible. Other prior MDS therapies, including but not limited to lenalidomide, erythroid stimulating agents, or similar RBC-, WBC-, or platelet direct therapies or growth factors, are allowed.
- 14) Patients who have not received strong and/or moderate cytochrome P450 enzyme (CYP) 3A inducers (eg, St. John's Wort) within 7 days prior to the initiation of study treatment.
- 15) Patients who have not consumed grapefruit, grapefruit products, Seville oranges (including marmalade containing Seville oranges) or starfruit within 3 days prior to the initiation of study treatment or are willing to discontinue consumption of these while receiving study drug.

CONFIDENTIAL Page 62 02 November 2023

16) Patients without malabsorption syndrome or other conditions that preclude enteral route of administration.

Safety Run-in Cohort 2 and Phase 2 Cohort 2 (R/R AML Mag+MEC)

In addition to meeting the inclusion criteria for all patients, patients who are enrolled into Safety Run-in Cohort 2 and Phase 2 Cohort 2 must fulfill the following cohort-specific inclusion criteria:

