5.3.6. Dose Modification and Delays for Mitoxantrone, Etoposide, and Cytarabine

MEC is a cytotoxic therapy and causes myelosuppression. Given that patients with AML will also be cytopenic as a result of their leukemia, dose modifications or delays of MEC should only occur if there is no evidence of leukemia, as defined by a bone marrow blast count of < 5% and absence of circulating peripheral blasts.

In the setting of absence of leukemic disease, treatment with MEC should be delayed in instances of ANC $< 500/\text{mm}^3$ or platelets $< 50,000/\text{mm}^3$ until recovery to an ANC $\ge 1000/\text{mm}^3$ or platelets $> 75,000/\text{mm}^3$ or ANC and platelet values equal to or above the patient's baseline values.

The individual components of the MEC regimen have distinct dose modification considerations and are detailed below

Mitoxantrone

Mitoxantrone clearance is reduced by hepatic impairment. Patients with total bilirubin > 3.5 mg/dL should reduce the dose of mitoxantrone by 50%. Mitoxantrone can be dosed at the full dose once total bilirubin is $\le 3.5 \text{ mg/dL}$.

Etoposide

Etoposide is renally metabolized and dose modifications should be made for impaired CLcr. If CLcr is 15 to 50 mL/min, administer 75% of the etoposide dose. If CLcr is < 15 mL/min, consider further dose reductions per institutional guidelines (ie, a 50% dose reduction).

Liver dysfunction may reduce the metabolism and increase the toxicity of etoposide; however, dose adjustment instructions are not provided in the US prescribing information (USPI). For patients with total bilirubin (predominantly direct) > 3 mg/dL or AST $> 5 \times$ ULN, administer 50% of the etoposide dose. Etoposide can be dosed at standard levels once total bilirubin is < 3 mg/dL or AST is $< 5 \times$ ULN.

Cytarabine

No dose adjustments are required for renal or hepatic impairment.

5.3.7. Prior and Concomitant Medications: Prohibited Concomitant Medications for Cohort 2

For the anti-leukemia regimens administered with magnolimab in this study, the current local or regional prescribing information should be consulted regarding permitted and prohibited concomitant medications.

Anti-leukemic therapies, including chemotherapy (with the exception of hydroxyurea), targeted therapies, and immunotherapy, are not permitted while patients are on study treatment.

Any investigational drugs other than magrolimab are prohibited during study treatment.

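### Appendix 8: the lower two Cockcroft-Gault rows print two conflicting creatinine units, neither of which fits their constants, so clearance is inflated about 10-fold or 88-fold if a printed unit is used

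*Protocol*

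**What the plan says.** Appendix 8 of the protocol tells sites how to choose a row: "The formula appropriate to the units in which serum creatinine was measured and the patient's gender should be used". It then gives four formulas, all with (140 − age) in the numerator. In the quotes below, numerator and denominator run on in one line.

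- Rows headed mg/dL: men "subject weight [kilograms] × 1 72 × subject serum creatinine [mg/dl"; women "subject weight [kilograms] × 0.85 72 × subject serum creatinine [mg/dl".
- Rows headed μM/dL: men "subject weight [kilograms] × 1.23 Subject serum creatinine [mg/dl"; women "subject weight [kilograms] × 1.04 Subject serum creatinine [mg/dl".

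Creatinine clearance (CLcr) is used in three places in the body:

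- Section 4.2, criterion 4, for all patients: "adequate renal function as demonstrated by a creatinine clearance (CLcr) ≥ 30 mL/min calculated by the Cockcroft-Gault formula".
- Section 4.2, criterion 11, as one of several ways to count as unfit in Cohort 1: "CLcr < 45 mL/min calculated by the Cockcroft-Gault formula".
- Section 5.3.6, for etoposide in Cohort 2: "If CLcr is 15 to 50 mL/min, administer 75% of the etoposide dose".

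Criteria 4 and 11 name the Cockcroft-Gault formula without citing Appendix 8. Section 5.3.6 names neither. Appendix 8 is the only place where the protocol writes the formula out.

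**The concern.** The lower two rows carry one unit in the heading and another in the denominator, so at least one must be wrong. The size of the constants suggests that both are. A formula meant for one creatinine unit and fed with another is wrong by the conversion factor between them, which here is one to two orders of magnitude and always upwards.

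The entry limit is a minimum, so inflated clearance lets through patients whom the limit is meant to keep out. The study plans about 35 centers globally (Synopsis), and the lower rows exist because results in units other than mg/dL were foreseen. A site whose laboratory reports μmol/L finds no row with its unit. Cohorts 1 and 3 are closed, but Cohort 2 is not (section 3.1.2), so the table still bears on current enrollment.

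**Working it through.** **Inputs.** From Appendix 8: the constants 1/72 and 0.85/72 (mg/dL rows, men and women) and 1.23 and 1.04 (lower rows). From section 4.2: the limit of 30 mL/min. One assumption from outside the protocol: creatinine has a molar mass of 113.12 g/mol, so 1 mg/dL = 88.4 μmol/L = 8.84 μmol/dL. The heading μM/dL is read as μmol/dL.

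**Step 1: reproduce the printed constants.** Convert the mg/dL rows to each candidate unit.

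| Creatinine in | Men | Women |
|---|---|---|
| μmol/L | 88.4 / 72 = 1.228 | 0.85 × 88.4 / 72 = 1.044 |
| μmol/dL (heading) | 8.84 / 72 = 0.123 | 0.85 × 8.84 / 72 = 0.104 |
| mg/dL (denominator) | 1 / 72 = 0.0139 | 0.85 / 72 = 0.0118 |

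The printed 1.23 and 1.04 are reproduced only for μmol/L, to within 0.4%.

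**Step 2: the same result without the outside figure.** Set each lower row equal to the mg/dL row above it. The creatinine number in the lower row must be 1.23 × 72 = 88.6 times (men) or 1.04 × 72 / 0.85 = 88.1 times (women) its mg/dL value. Entering mg/dL, as the lower denominators say, is therefore wrong by these factors on the appendix's own figures.

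**Step 3: inflation for each printed unit** (printed constant divided by the constant that fits the unit).

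- mg/dL entered: 88.6 (men), 88.1 (women).
- μmol/dL entered: 10.02 (men), 9.97 (women).
- μmol/L entered: 1.00.

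**Step 4: effect on the 30 mL/min limit.** Under the printed units, a calculated 30 corresponds to a true clearance of 30 / 88.6 = 0.34 mL/min (mg/dL entered) or 30 / 10.02 = 3.0 mL/min (μmol/dL entered).

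**Step 5: example.** Man, 70 years, 70 kg, creatinine 2.5 mg/dL = 22.1 μmol/dL = 221 μmol/L; (140 − 70) × 70 = 4900.

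| Row and unit entered | Calculation | CLcr, mL/min | Below 30? |
|---|---|---|---|
| mg/dL row, mg/dL | 4900 / (72 × 2.5) | 27.2 | yes |
| Lower row, mg/dL | 4900 × 1.23 / 2.5 | 2411 | no |
| Lower row, μmol/dL | 4900 × 1.23 / 22.1 | 273 | no |
| Lower row, μmol/L | 4900 × 1.23 / 221 | 27.3 | yes |

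In the mg/dL row this man falls below 30 once creatinine exceeds 4900 / (72 × 30) = 2.27 mg/dL. In the lower row he would need more than 4900 × 1.23 / 30 = 201 mg/dL (mg/dL entered), or 4900 × 1.23 / 30 / 8.84 = 22.7 mg/dL (μmol/dL entered).

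**Step 6: the other two uses, if Appendix 8 is applied to them.** For the Cohort 1 criterion the direction is reversed. It asks for clearance below 45, so inflation takes this route to eligibility away. A true 40 would be calculated as about 400 or 3,500. For section 5.3.6, a true clearance of 15 to 50 would be calculated as about 150 to 500 (10-fold), or higher still at 88-fold, and so would fall in none of the listed bands.

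**The case against.** The strongest reply is that the appendix, sensibly used, gives the right answer. A site with mg/dL results is sent to the mg/dL rows, which are correct. A site whose laboratory reports μmol/L and enters that number in the lower row is also right. To reach 88-fold, a site must hold or convert to mg/dL and still use the row that is not headed mg/dL. To reach 10-fold, it must hold or convert to μmol/dL. A result such as 2411 mL/min is also visibly impossible. Sites may use their own calculator, since no body section cites Appendix 8. All of this stands, and it limits how often the error would bite. It does not make the table right: a careful site that converts its result to match a printed unit is the one that goes wrong, and a 10-fold error is less conspicuous than an 88-fold one.

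Three stronger readings are tempting, and the protocol does not support them.

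- A reader might infer that the renal entry limit cannot exclude anyone. It works wherever the mg/dL rows are used or μmol/L is entered. Even at 10-fold, a true clearance below about 3 mL/min is still excluded.
- A reader might infer that sites reporting SI units would pass every patient. That depends on which number they enter, and for the Cohort 1 criterion the error works the other way.
- A reader might infer that Appendix 8 governs the etoposide bands. Section 5.3.6 does not say how clearance is to be calculated, so this is a possibility only.

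A unit lost in reproducing the table is an unlikely explanation, because both lower denominators show the same wrong unit.

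**Conclusion.** The lower two rows of Appendix 8 are mislabelled. Heading and denominators contradict each other, and neither printed unit fits the constants, which belong to μmol/L. If a printed unit is followed, clearance is inflated about 10-fold (heading) or about 88-fold (denominators). These are two separate readings, not the ends of a range. For patients calculated that way, the 30 mL/min entry limit has practically no force.

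The 88-fold figure follows from the appendix alone. The 10-fold figure, and the identification of the unit as μmol/L, rest on 1 mg/dL = 88.4 μmol/L. The appendix's own constants imply 88.1 to 88.6, so the conclusion is not sensitive to that assumption.

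The prospective effect is confined to Cohort 2. Cohort 1 is closed with 18 patients enrolled, and Cohort 3 closed with none. Nothing in the protocol shows that any patient's clearance was miscalculated, and no endpoint, analysis set, test or power figure depends on this point. It should still be corrected, because it is the only written-out formula behind an entry criterion that protects patients.

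**What to change.** In Appendix 8, change the heading of the lower two rows and both of their denominators to μmol/L. The constants 1.23 and 1.04 stay as they are. Ask sites which row and which unit they used, and recheck clearance for enrolled patients where the lower rows were used with a unit other than μmol/L. If Appendix 8 is meant to govern criteria 4 and 11 and section 5.3.6, a cross-reference there would settle it.

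The cost is a correction to one table, plus a short query to sites. The entry limit and the clearance bands themselves do not change.
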